13.4.5 Descriptive Analyses

Baseline and demographic characteristics will be compared between groups using a ranksum test for continuous variables and a Fisher exact test for binary/categorical variables. The relationship between demographic and other characteristics and antibody levels will be explored.

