This study will investigate the effect of an additional dose of either the Moderna or Pfizer-BioNTech COVID-19 vaccine, with or without a reduction in immunosuppression, in participants who demonstrate a negative or low (≤ 2500 U/mL) anti-RBD titer after a completed mRNA COVID-19 vaccine series. Response will be assessed using the Roche Elecsys® anti-SARS-CoV-2 S assay which has an approximate 1:1 conversion to World Health Organization binding antibody units (BAU). Anti-S1/RBD levels are well correlated with neutralizing antibody against SARS-CoV-2 and with vaccine sero-protection in the general population.^{37,38} The precise cutoff that connotes protection from infection is not established for immunocompromised persons. Early studies, however, indicated anti-S1/RBD levels of 15-144 BAU⁴⁰ are correlated with live virus neutralization of ancestral variants in convalescent persons. Subsequent analyses of vaccine efficacy across trials indicated a level 2-4-fold higher for vaccine-evoked neutralization (compared to convalescents) best correlates with vaccine efficacy.⁴¹ Consistent with this, several studies in transplant recipients have suggested anti-S1/RBD levels of 100-250 BAU after vaccination as associated with in vitro neutralization; below this level, neutralizing capacity against SARS-CoV-2 variants is not reliable and suggests higher risk of infection. Notably, variants of concern, particularly the Omicron variant and its sublineages demonstrate significant immune evasion and need for 10-20-fold higher levels of antibody to neutralize than required for ancestral variants.⁵²⁻⁵⁵ Version 6.0 of the protocol increases the SARS-CoV-2 S titer for eligibility from 250 U/mL to 2500 U/mL to account for the findings that suggest the antibody levels needed to neutralize Omicron are significantly higher.⁵⁸

Rationale for Selection of Investigational Product or Intervention

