2.5 Secondary Immunogenicity Objectives

To assess whether responses to additional doses of COVID-19 vaccine are improved by temporary reduction or withholding of immunosuppressive medications around the time of vaccine.

To assess whether response to an additional dose of COVID-19 vaccine is associated with clinical phenotype (e.g., age, organ type, time post-transplant, immunosuppressive regimen).

To evaluate durability of response over 1-year in those who have an antibody response to the additional dose of vaccine.

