6.1 Investigational Agent #1: Moderna COVID-19 Monovalent Vaccine (Protocol v1.0-5.0)

The Moderna COVID-19 monovalent vaccine will no longer be offered for the study.

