6.2 Investigational Agent #2: Pfizer-BioNTech COVID-19 Monovalent Vaccine (Protocol v1.0-5.0)

The Pfizer-BioNTech COVID-19 monovalent vaccine will no longer be offered for the study.

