6.3 Investigational Product #3: Moderna Bivalent COVID-19 Vaccine (Protocol v6.0-7.0)

The Moderna Bivalent COVID-19 Vaccine (Original and Omicron BA.4/BA.5), hereafter referred to as Moderna Bivalent COVID-19 Vaccine will no longer be offered for this study

Commented [MOU1]: I can either add sections addressing the adapted monovalent vaccines or we modify this section to be generic and refer to the most current vaccine?

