12.2 Definitions

12.2.1 Adverse Event (AE)

Any untoward or unfavorable medical occurrence associated with the subject's participation in the research, whether or not considered related to the subject's participation in the research (modified from the definition of adverse events in the 1996 International Conference on Harmonization E-6 Guidelines for Good Clinical Practice) (from OHRP "Guidance on Reviewing and Reporting Unanticipated Problems Involving Risks to Subjects or Others and Adverse Events (1/15/07)" <http://www.hhs.gov/ohrp/policy/advevntguid.html#Q2>)

For this study, adverse events will be considered for association with the additional dose of COVID-19 vaccine and study mandated procedures as follows:

Vaccine Administration (Moderna COVID-19 Vaccine (monovalent, bivalent, and 2023-2024 formula as per protocol version), Pfizer-BioNTech COVID-19 Vaccine (monovalent, bivalent, and 2023-2024 formula as per protocol version)

All AEs occurring within 30 days following a single COVID-19 vaccine dose and SAEs up to 6 months post vaccine administration.

Study mandated procedures:

Any AE occurring within 24 hours of a protocol mandated blood draw
Any AE occurring within 24 hours of a protocol mandated nasal swab
Any AE occurring within 24 hours of an oral fluid collection
Any AE occurring during the period from the onset of immunosuppression reduction until 30 days after return to full immunosuppression and SAEs up to 6 months post return to full immunosuppression.

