13.4.2 Primary Analysis of Primary Endpoint(s)/Outcome(s)

The primary endpoint is a continuous measurement. All individuals whose primary endpoint is measured will be included in the analysis population.

For the comparison of immunoreduction vs no immunoreduction, we will reject the null hypothesis if the two-sided rank-sum p value comparing the -fold increase between the two groups falls below 0.05.

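### Enrolment spans three vaccine formulations and a tenfold rise in the titre ceiling, but Section 13 uses neither: the randomised test stays valid yet may lose precision, and the non-randomised associations can be confounded by era.

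*Combined protocol and SAP*

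**What the plan says.** Formulation follows protocol version. Sections 6.1 and 6.2, both labelled v1.0-5.0, retire the monovalent products: "The Moderna COVID-19 monovalent vaccine will no longer be offered for the study" and "The Pfizer-BioNTech COVID-19 monovalent vaccine will no longer be offered for the study". Section 6.3 is headed "Investigational Product #3: Moderna Bivalent COVID-19 Vaccine (Protocol v6.0-7.0", and 6.4 is its Pfizer-BioNTech counterpart. Sections 6.5 and 6.6 bring in the 2023-2024 (XBB.1.5) formula from v8.0. Section 12.2.1 covers all three within this one study: "monovalent, bivalent, and 2023-2024 formula as per protocol version".

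Eligibility changed at the same point as the bivalent switch. Section 1.1 states: "Version 6.0 of the protocol increases the SARS-CoV-2 S titer for eligibility from 250 U/mL to 2500 U/mL".

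The analysis plan names none of this:
- 13.3 randomises the immunosuppression reduction by site and by pre-dose titre (<50 vs ≥50 U/mL).
- 13.4.2 rejects the null if the "two-sided rank-sum p value comparing the -fold increase between the two groups falls below 0.05", with no strata.
- 13.4.4 splits antibody response by interval since the last dose and by Pfizer vs Moderna, not by formulation.
- 13.4.5 says that "The relationship between demographic and other characteristics and antibody levels will be explored", with no model or covariates.

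Section 2.5 makes it a secondary objective to ask whether response is "associated with clinical phenotype (e.g., age, organ type, time post-transplant, immunosuppressive regimen").

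**The concern.** Fold-rise has two reasons to differ between eras: the antigen changed, and so did the range of titres admitted. The protocol's own background (1.3) reports that recipients with low but detectable antibody reached levels about 5-fold higher after a further dose than seronegative recipients did, so response depends on the starting point. The endpoint is a ratio to baseline with a floor at 10 U/mL (13.2), so the baseline mix also enters directly. The randomisation stratum at 50 U/mL does not separate 50-250 from 251-2500.

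Two things are at stake. In the arm comparison, era is spread evenly by randomisation, but any between-era spread sits in the ranks as noise. In the phenotype objective and the 13.4.4 and 13.4.5 analyses, the groups compared are not randomised. A characteristic that became more or less common over the study would then appear to predict response only because later participants received a different vaccine under a different ceiling.

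**Working it through.** **Inputs from the documents.** 200 per arm, two-sided α 0.05, log-normal fold changes, 80% power at a ratio of 1.2 (13.7). Not given: the SD of ln(fold), enrolment per era, response per era. These are assumed below.

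**1. The plan's own figure.** The large-sample power of the rank-sum test is

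power = Φ( ln R / (SD × √(π/3) × √(2/200)) − 1.96 ), with √(π/3) = 1.023 and √(2/200) = 0.1.

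Setting power to 80% at R = 1.2 gives SD = 0.1823 / (2.80 × 1.023 × 0.1) = 0.636. Simulation at this SD returns 79%. The stated 80% can be matched only by choosing this SD.

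**2. Power forgone.** Take three equal eras with fold-rise evenly graded from first to last by a factor f. The era variance of ln(fold) is (2/3) × (½ ln f)²:
- f = 1.5: (2/3) × 0.2027² = 0.027
- f = 2: (2/3) × 0.3466² = 0.080

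The pooled test sees the total SD; the era-stratified test sees approximately the within-era SD. The SD of 0.636 can be read in two ways. A larger SD of 1.25, with its own 80%-power ratio of 1.43, is added for range.

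| SD reading | f | Within-era SD | Total SD | Pooled | Stratified |
|---|---|---|---|---|---|
| 0.636 is within-era | 1.5 | 0.636 | 0.657 | 77% | 80% |
| 0.636 is within-era | 2 | 0.636 | 0.696 | 73% | 80% |
| 0.636 is whole-arm | 1.5 | 0.614 | 0.636 | 80% | 83% |
| 0.636 is whole-arm | 2 | 0.570 | 0.636 | 80% | 88% |
| 1.25 is within-era | 1.5 | 1.25 | 1.261 | 79% | 80% |
| 1.25 is within-era | 2 | 1.25 | 1.282 | 78% | 80% |

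Simulations agree to within about 3 points; for the whole-arm reading at f = 2 they gave 77-80% pooled against 85-87% stratified. The loss is therefore about 1-3 points at 1.5-fold and 2-9 points at 2-fold. The pattern matters: if one era alone is 2-fold higher (2:1:1) and 0.636 is within-era, simulation gives 69% against 80%. With no era difference, stratifying costs under 1 point (79.3% against 78.9%).

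**3. Validity.** With no treatment effect and eras at 3:1:1.5, simulated type I error is 5.0% pooled and 4.9% stratified.

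**4. Spurious associations.** Let a characteristic with no effect have prevalence 30/50/70% over equal eras. Carriers are spread over the eras 0.200/0.333/0.467 and non-carriers 0.467/0.333/0.200. The difference in mean ln(fold) is (0.467 − 0.200) × ln f = 0.267 ln f, so the apparent ratio is exp(0.267 ln f). For 40/50/60% the multiplier is 0.400 − 0.267 = 0.133.

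| Prevalence | f = 1.5 | f = 2 |
|---|---|---|
| 30/50/70% | 1.11 | 1.20 |
| 40/50/60% | 1.06 | 1.10 |

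In simulation (within-era SD 0.636, first era 2-fold higher), the null characteristic reached p < 0.05 in 74% of trials at 30/50/70% and 25% at 40/50/60%. Stratifying by era returned both to 5%.

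**The case against.** The strongest reply is that nothing here is invalid. An unstratified rank-sum is a legitimate test of a randomised contrast, so moving to van Elteren is a matter of efficiency. Every era input is assumed, small era differences cost little, and unequal eras can cost less: with shares of 5/15/80% and a 2-fold difference, simulation gave 76% against 79%. No text suggests that age, organ type or regimen drifted by 40 percentage points. Section 13.4.5 is openly descriptive, and its reference to other characteristics could be taken to include formulation. The synopsis also gives accrual as 4 months, which sits oddly with three successive formulations and should be reconciled. All of this limits the size of the point. It does not supply an era term, and the phenotype question is a stated secondary objective.

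A reader might infer more than the documents support:
- *That power falls to 54-60%.* This needs 3- to 4-fold era differences, and it needs the back-solved SD of 0.636 to be within-era. Section 13.7 speaks of the distribution of fold changes in each group, which reads more naturally as the whole arm, era spread included. On that reading the result is a forgone gain, not a fall below 80%.
- *That baseline titres of 251-2500 occur only from v6.0.* The ceiling applies to the screening titre, and 8.2 allows an earlier result to be used. The endpoint's baseline is the pre-dose titre, which can differ. Section 1.1 reports only the change at v6.0, not the ceiling through every earlier version.
- *That Section 13 was left behind by the amendments.* The text shows only that it contains no era term, not why.

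**Conclusion.** The point stands as an inexpensive improvement to the analysis, worth making before database lock. It is not a threat to the validity of the primary result. The documents establish that formulation and the titre ceiling changed with protocol version and that no analysis in Section 13 conditions on either. They do not establish that fold-rise differed between eras, or by how much. Assuming equal eras, the power forgone is about 1-3 points for a 1.5-fold difference and about 2-9 points for an evenly graded 2-fold difference, somewhat more if a single era stands apart, and nil if eras are alike. The more consequential part is confounding of the association analyses. A 2-fold era difference with a 30/50/70% drift in prevalence gives a spurious ratio of about 1.2, the size of effect that 13.7 aims to detect; a 40/50/60% drift gives about 1.1.

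**What to change.** - **13.4.2:** replace the unstratified rank-sum with a van Elteren test stratified by formulation era (v1-5 monovalent, v6-7 bivalent, v8+ 2023-2024 formula) and by the randomisation titre stratum (<50 vs ≥50 U/mL). Define era by the version in force at randomisation, so that it is a baseline factor. The 3 × 2 = 6 strata average about 67 participants each.
- **2.5 objective, 13.4.4 and 13.4.5:** include era and log baseline titre as covariates. State that era alone cannot separate the ceiling change from the bivalent switch, since both came at v6.0; baseline titre addresses the ceiling directly.
- **Reporting:** add a supporting table of enrolment and arm effect by era.

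The cost is SAP wording. Vaccine administration details already go on the eCRF (6.5.2, 6.6.2), and the titre stratum is held from randomisation. If eras do not differ, stratifying by era costs under 1 point of power.

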13.5 Interim Analyses

13.5.1 Interim Analysis of Efficacy Data

An interim efficacy analysis is not planned for this trial, because (1) It is extremely unlikely that a definitive difference between arms would emerge at a time when it is still possible to stop enrollment, and (2) it is desirable to be able to evaluate safety outcomes in the full cohort, assuming that no safety stopping rules are met. However, at the time of the safety interim analyses, the DSMB will be provided concurrent SARS-CoV-2 antibody results in each arm to aid in evaluating the risk/benefit calculus.

13.5.2 Interim Analysis of Safety Data

Excess incidence of dnDSA in kidney transplant recipients: An interim analysis will be performed to look for evidence of an excess incidence of dnDSA in the IS reduction groups (those undergoing withdrawal of MMF; and those undergoing a decrease in CNI dose) as compared with those receiving an additional dose of vaccine alone. When fifteen subjects in each of these groups have reached day 30 in the study (study visit 4), the core HLA lab will determine whether de novo DSA is present. We will perform a similar analysis when fifty subjects in each group have reached day 30. At each of these two time points, the proportion with Class II dnDSA in each IS reduction group will be compared with the COVID-19 vaccine dose alone group using a one-sided Fisher exact test to determine if there is an excess incidence of Class II dnDSA, and the results presented to the DSMB for review

[figure not shown]

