3.3 Secondary Endpoints

3.3.1 Secondary Safety Endpoints

Local and systemic vaccine reactogenicity and/or allergy
Serious adverse events occurring during the 30 days following the additional dose of vaccine
Treated acute cell-mediated and/or antibody-mediated allograft rejection (clinical or biopsy-proven) within 60 days following the additional dose of vaccine
Development of de novo donor-specific anti-HLA antibody within 90 days of the vaccine
Graft loss within 60 days of the vaccine
Death within 60 days of the vaccine

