5.3 Risks Associated with IS Reduction

Any decrease in dose or frequency of immunosuppressive medications in a transplant recipient carries the risk of alloimmune activation leading to acute cellular rejection, subclinical rejection, acute or chronic antibody-mediated rejection, and/or the formation of de novo DSA. The inclusion criteria and the specific immunomodulatory strategies have been designed to minimize, but do not eliminate, this risk. Study participants undergoing IS reduction will be closely monitored for evidence of graft injury and will be returned to their baseline immunosuppressive regimen should graft injury be evident. In addition, subjects will be monitored for the development of de novo DSA throughout the study period.

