6.7 Immunosuppression Reduction

6.7.1 Immunosuppression (IS) Reduction

Participants on a tacrolimus-based regimen that includes MMF (or equivalent), with or without corticosteroid:

MMF (or equivalent) will be withheld for five days prior to and 2 weeks following vaccine administration. During the interval that MMF is withheld, no adjustments will be made to the CNI or corticosteroid dose.

Participants on a tacrolimus based regimen with a trough level ≥ 5 ng/mL, with or without ≤ 5 mg Prednisone (or equivalent) and no MMF or other antimetabolite

Reduce CNI by 25% of starting dose for 5 days prior to and 2 weeks following vaccine administration.

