12.7.2 DSMB Review

12.7.2.1 Planned DSMB Reviews

The Data and Safety Monitoring Board (DSMB) shall review safety data one month after all study participants have received study vaccine, unless a safety event requires earlier review. They will review the study again when the database is locked after the last patient's last visit. Interim DSMB reviews may occur at any time at the discretion of the medical monitor or the protocol chair. Data for the planned safety reviews will include, at a minimum, a listing of all reported AEs and SAEs.

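### The two interim dnDSA looks are keyed to Day 30, and no planned DSMB comparison during enrolment is required to use the Month 3 draw, although the safety endpoint runs to 90 days

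*Combined protocol and SAP*

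**What the plan says.** The secondary safety endpoint in section 3.3.1 is "Development of de novo donor-specific anti-HLA antibody within 90 days of the vaccine", and section 13.2 repeats the 90-day horizon. Both forms of reduction stop two weeks after vaccination (section 6.7.1): "MMF (or equivalent) will be withheld for five days prior to and 2 weeks following vaccine administration" and "Reduce CNI by 25% of starting dose for 5 days prior to and 2 weeks following vaccine administration".

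Section 13.5.2 sets the first look as follows: "When fifteen subjects in each of these groups have reached day 30 in the study (study visit 4"), at which point the core HLA laboratory determines dnDSA. For the second it says "We will perform a similar analysis when fifty subjects in each group have reached day 30". At each look, each reduction group is compared with vaccine alone "using a one-sided Fisher exact test to determine if there is an excess incidence of Class II dnDSA", and the result goes to the DSMB. The text gives no significance threshold. A figure that follows it is not shown in the copy reviewed.

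Appendices 2 and 3 schedule DSA for kidney recipients at Week 4 and Months 3, 6 and 12 in both arms. The pausing rules in section 11.5 cover rejection, graft loss and death by group, but not dnDSA. Apart from these looks, section 12.7.2.1 plans DSMB reviews one month after the last vaccination and at database lock: "Data for the planned safety reviews will include, at a minimum, a listing of all reported AEs and SAEs". Section 5.3 states that "subjects will be monitored for the development of de novo DSA throughout the study period".

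**The concern.** The two looks are the only prespecified between-group comparison of dnDSA while participants are still being assigned to reduction. They are triggered by Day 30 and read most naturally as Day 30 status. A sample taken about two weeks after reduction ends may miss antibody that appears later but still within the 90-day endpoint. If an excess emerged mainly between Day 30 and Day 90, the DSMB could be shown no excess at look 2 even though Month 3 results for some of the same participants were available. The monitoring promised in section 5.3 is not carried into any planned group comparison on the endpoint's own time scale.

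**Working it through.** The plan states no power, threshold or boundary for these looks, so there is no figure to reproduce. The check has three parts.

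**1. Window arithmetic.** Week 4 is Day 28 ± 3 (section 8.7), that is Day 25 to 31. Reduction ends at Day 14, so the sample falls 11 to 17 days later. Day 28 covers 28/90 = 31% of the endpoint window, and (28 − 14)/(90 − 14) = 14/76 = 18% of the part after reduction ends.

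**2. How many Month 3 results exist at each look.** From the documents: 400 participants, 200 per arm (13.7) and 4 months' accrual (synopsis). Assumed: uniform accrual, vaccination at entry, Day 30 taken as one month, and 50 to 100 kidney recipients in the smallest reduction group (the MMF/CNI split and kidney share are not given). For a group of size G accrued over A months, the look at n falls at n·A/G + 1 months. The share of the first n with a Month 3 sample is (look time − 3)·(G/A)/n, or zero if negative.

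| Accrual | G | Look 2 at month | First 50 with Month 3 | Still to enrol (of 400) |
|---|---|---|---|---|
| 4 months | 100 | 2.0 + 1 = 3.0 | 0% | 100 |
| 4 months | 70 | 2.86 + 1 = 3.86 | 0.86 × 17.5 = 15, or 30% | about 14 |
| 4 months | 50 | 4.0 + 1 = 5.0 | 2.0 × 12.5 = 25, or 50% | 0 (closed at month 4) |
| 12 months | 100 | 6.0 + 1 = 7.0 | 4.0 × 8.33 = 33, or 67% | 400 × 5/12 = 167 |

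Look 1 under 4-month accrual falls at 15 × 4/100 + 1 = month 1.6 (G = 100) to 15 × 4/50 + 1 = month 2.2 (G = 50), before any Month 3 sample. The 50% row arises only after enrolment has closed and, at month 5, after the last reduction has ended (about month 4.5).

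At the review one month after the last vaccination (about month 5 under 4-month accrual), participants vaccinated in the first 2 of 4 months, about 200 of 400, have passed Month 3.

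**3. What counting Month 3 adds at look 2 (illustration only).** Assumed: 90-day risk 15% with reduction and 2% in control, 50 v 50, exact one-sided Fisher test at 0.05. Let f be the share of 90-day events visible by the Week 4 sample and m the share of participants with Month 3 in hand. Visible share v = f + (1 − f)·m; event probabilities are 0.15v and 0.02v.

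| f | m | v | Risks compared | Power |
|---|---|---|---|---|
| 0.31 (even spread) | 0 | 0.31 | 4.7% v 0.6% | 6% |
| 0.31 | 0.30 | 0.52 | 7.8% v 1.0% | 24% |
| 0.31 | 0.67 | 0.77 | 11.6% v 1.5% | 48% |
| 0.75 (early onset) | 0 | 0.75 | 11.3% v 1.5% | 46% |
| 0.75 | 0.67 | 0.92 | 13.8% v 1.8% | 60% |

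With every 90-day event visible, power is 66% at 50 v 50 but only 13% at 15 v 15. With no control events, the test needs 4 of 15 (p = 0.0498) or 5 of 50 (p = 0.028) in the reduction group. The time horizon is therefore not the main limit at look 1.

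**The case against.** A reader might infer that Month 3 results are excluded and can never reach the DSMB. The documents do not say so. In section 13.5.2, Day 30 is the trigger, and no sentence limits the data to the Week 4 sample. Section 12.7.2.1 allows interim DSMB reviews at any time at the discretion of the medical monitor or protocol chair, and the AE/SAE listing is a minimum. What stands is an unspecified data cut and the absence of any commitment to the 90-day horizon.

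A reader might also infer that alloimmune harm is otherwise unmonitored. It is not: the rejection and graft-loss pausing rules apply by group, and DSA is followed in individuals throughout. Those rules count events against an expected rate. They do not compare groups and do not include dnDSA.

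The strongest objection is that under the only stated accrual period, 4 months, little is lost. That is correct. The successive vaccine generations across protocol versions (section 6) suggest longer accrual but do not quantify it. The power contrast also rests on assumed risks, onset pattern and threshold, and it narrows if most dnDSA appears early. The missing figure may hold operating details for these looks.

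Finally, counting Month 3 results gives unequal follow-up if groups fill at different rates. That is a real cost, and it must be shown.

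**Conclusion.** The point holds as a gap in specification. Both looks are keyed to Day 30, about two weeks after reduction ends. The endpoint is 90 days, and no planned between-group comparison for the DSMB is committed to the Month 3 draw while enrolment is open.

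The size depends on accrual. Under the stated 4 months it is small: nothing at look 1, and 0-30% of the first 50 at look 2 before enrolment closes. It becomes material if accrual is slower: 67% at look 2, with about 167 still to enrol, at 12 months and 100 per reduction group. The gain in power at look 2 could then be from 6% to 48%, or from 46% to 60% if three quarters of events are visible by Day 30. With 30% in hand, the first figure rises to 24%. All of these rest on the assumed 15% v 2% risk and a 0.05 threshold.

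Counting all scheduled results cannot show the DSMB fewer events than a Day 30 reading would. This is a cheap improvement, not a flaw that undermines the trial.

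**What to change.** In section 13.5.2, keep the triggers at 15 and 50 per group. State that each look counts cumulative Class II dnDSA on all scheduled DSA samples (Week 4 and Month 3) resulted by the data cut. Show Day 30 and Month 3 proportions by group, with the number assessed at each. Label the Month 3 column by visit, because its ± 2-week window can run past Day 90. In section 12.7.2.1, add the same table to the review one month after the last vaccination.

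Use scheduled draws only: in the schedules as reviewed, for-cause DSA is marked in Appendix 2 but not in Appendix 3, so including it could make ascertainment unequal. Also correct the reference to study visit 4. Week 4 is visit 06 in Appendix 2 and visit 07 in Appendix 3, while visit 04 is Week 2 and Week 1 respectively, with no DSA draw at either.

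The cost is a few sentences and no new samples. The core HLA laboratory must result Month 3 samples in time for each look, and any difference in follow-up between groups at the cut must be reported beside the comparison.
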